1.0 Objectives*

Two-thirds of the US population, particularly African Americans (AA), is at risk for inadequate or deficient 25-hydroxy-vitamin D (25(OH)VD). Epidemiological studies demonstrate an association between better health outcomes and higher blood levels of 25(OH)VD. Randomized controlled clinical trials have shown that, while supraphysiological high doses of VD are needed to achieve adequate blood levels of 25(OH)VD, not all subjects respond to them. Recent studies have also questioned the therapeutic effects of high-dose VD supplementation. This application presents our design for a randomized, double-blind, placebo-controlled clinical trial to test the hypothesis that supplementation with VD in combination with L-cysteine (LC) is more successful at optimizing the statuses of 25(OH)VD [biological signatures] and simultaneously decreasing TNF- α and IR [functional or clinical outcomes], suggesting a better therapeutic approach compared with supplementation with VD alone in AA subjects.

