2.0 Background*

Previous human studies report that VD supplementation increases circulating 25(OH)VD status but has limited success in reducing insulin resistance (IR). Other human studies report that supplementation with LC lowers TNF- α and IR. This clinical trial will determine the impact of combined supplementation with VD+LC on increases in levels of 25(OH)VD as well as simultaneous reduction in TNF- α and IR biomarkers (mediators of clinical benefit) in the AA population. The mechanistic focus of this clinical trial will determine whether combined supplementation with VD and LC provides a more successful approach to increasing 25(OH)VD [biological signatures] as well as simultaneously decreasing TNF- α and IR [functional or clinical outcomes], compared with supplementation with VD alone. If the results are positive, future studies will investigate potential of this approach to reduce the inflammation, pain, and other health issues among AA in a full-scale efficacy trial.

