10.0 Data Management* and Confidentiality

Analyses of data will be performed by the biostatistician, [name]. A *p*-value of less than 0.05 for a statistical test will be considered significant. Data will be analyzed statistically to compare the 4 groups at baseline and various visits using ANOVA. The Wilcoxon signed-rank or paired *t*-test will be used to determine significant changes after supplementation for each treatment group, and the ANOVA test to compare the 4 treatment groups on changes. The results for the pairwise comparisons among the 4 time points will determine whether there is a significant change in the outcome variables over time. The effect of covariates or possible confounders (age, sex, BMI, initial levels of outcomes, etc.) will be controlled for and tested for their significant effects by including them in the repeated measures model used.

Based on animal studies, co-supplementation with LC+VD will be more successful and raise serum 25(OH)VD levels by nearly 30 ng/mL(17, 18). Our goal is to raise circulating 25(OH)VD levels by an average of 30 ng/mL, and reduce IR levels by 35% in all AA subjects receiving combined VD+LC supplementation. To observe a significant response or change, a sample size of 7 for 25(OH)VD, and 27 for IR were considered adequate using a paired *t*-test conducted at 5% level of significance and 80% power. We chose a goal of 30 subjects in each group who complete the study in the VD+LC supplementation and other groups. Based on our experience from a previously completed clinical trial (H-09-073), enrollment of and consent from 160 AA volunteers who participate in blood collection for screening should give us more than the required sample size of 30 subjects in each group (120 in 4 groups) after factoring in a dropout rate of about 16% for screen failures, withdrawal before randomization, or those who did not complete all the visits. Our experience also suggests that nearly 190 subjects will need to be contacted to achieve our goal of 160 AA volunteers who complete the written consent form and are enrolled in this clinical trial. This takes into account the fact that only about 85% of those initially contacted will indeed show up for the screening visit and complete the written informed consent.

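### Section 10.0 names no test of VD+LC against VD alone, which is the trial's hypothesis, and its sample size answers a different question

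*Protocol*

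**What the plan says.** Section 1.0 expects the combination to do better on 25(OH)VD, TNF-α and insulin resistance (IR), "suggesting a better therapeutic approach compared with supplementation with VD alone in AA subjects". Section 2.0 repeats the same comparator. It also says of earlier human studies that "VD supplementation increases circulating 25(OH)VD status but has limited success in reducing insulin resistance (IR").

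Section 10.0 lists these analyses, each judged at p<0.05:

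- ANOVA across the four groups at baseline and at visits;
- Wilcoxon signed-rank or paired t-tests "to determine significant changes after supplementation for each treatment group";
- "the ANOVA test to compare the 4 treatment groups on changes";
- "pairwise comparisons among the 4 time points will determine whether there is a significant change";
- a repeated measures model, mentioned for controlling and testing covariates.

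On sample size it sets goals for the VD+LC arm of a 30 ng/mL rise in 25(OH)VD and a 35% fall in IR. It then says: "To observe a significant response or change, a sample size of 7 for 25(OH)VD, and 27 for IR were considered adequate", by a paired t-test at the 5% level with 80% power. The target is 30 completers per arm.

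**The concern.** The only pairwise comparisons named are between time points, not between arms. The between-arm tests are global: they ask whether all four means are equal, not whether VD+LC differs from VD.

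For 25(OH)VD this matters in practice. The placebo and LC arms get no vitamin D and the other two arms do. If VD raises 25(OH)VD, as section 2.0 says it does, the global ANOVA and the before/after test in the VD+LC arm can both be significant with no L-cysteine effect. Either result could then be read as support for the combination.

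For HOMA-IR and TNF-α the problem is narrower: the hypothesis has no stated test. Excess rejections there would need VD or time to have an effect of its own.

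The power statement has the same fault. It describes change within one arm, so the reader cannot tell what 30 per arm delivers for VD+LC versus VD.

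**Working it through.** **Inputs.** From section 10.0: n=7 for 30 ng/mL, n=27 for 35%, 80% power, 5% level, 30 completers per arm. Assumed, because the protocol does not give them: two-sided tests; the 30 ng/mL and 35% goals as the planning effects; IR change in percentage points of baseline; a VD effect D of 5 to 20 ng/mL, equal in both VD arms; L-cysteine with no effect.

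**1. The plan's own figures.** They cannot be reproduced without an SD, but they can be solved backwards. By the noncentral t with n−1 df and noncentrality d√n:

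- n=7 gives d = 1.273, so SD = 30/1.273 = 23.6 ng/mL. Taking n=6 gives 20.9, and the normal approximation at n=7 gives 28.3, hence a range of about 21 to 28.
- n=27 gives d = 0.560, so SD = 35/0.560 = 62.5 points (61.2 with n=26; 64.9 by the normal approximation).

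**2. The named tests on 25(OH)VD when L-cysteine adds nothing.** Mean changes are 0, 0, D, D with 30 per arm. The ANOVA noncentrality is 30 × 4 × (D/2)²/SD² = 30D²/SD², on 3 and 116 df. At D=10 and SD 23.6 it is 30 × 100/557 = 5.4. The before/after test in VD+LC has noncentrality D√30/SD.

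| D (ng/mL) | ANOVA, SD 21 | ANOVA, SD 23.6 | ANOVA, SD 28 | VD+LC before/after, SD 23.6 |
|---|---|---|---|---|
| 5 | 16% | 14% | 11% | 20% |
| 10 | 56% | 46% | 33% | 61% |
| 15 | 91% | 83% | 67% | 92% |
| 20 | 99.5% | 98% | 91% | 99% |

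Over the same SD range the before/after test runs from 16% to 99.9%. A smaller SD raises the rates: at SD 15 and D=10 the ANOVA is significant in 87% and the before/after test in 94%. Simulation (20,000 trials per setting, SD 23.6, D=10, 15 and 20) agrees with the ANOVA formula to within about half a percentage point. A direct two-sample test of VD+LC versus VD rejected in 4.9% to 5.2%. For IR with no VD effect, the ANOVA stays at 5%.

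**3. What 30 per arm gives for VD+LC versus VD.** Two-sample t, 58 df, noncentrality d√(30/2), no baseline adjustment:

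- 80% power needs d = 0.736.
- 25(OH)VD: 0.736 × 23.6 = 17.4 ng/mL (15.4 at SD 20.9; 20.8 at SD 28.3).
- IR: 0.736 × 62.5 = 46 points (45 to 48 over the SD range), more than the whole 35% goal.
- If all of the 35% were the between-arm difference, d = 0.560, the noncentrality is 0.560 × 3.873 = 2.17 and power is 57%. At that d, 51 per arm falls just short of 80% (79.99%) and 52 reaches it.

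**The case against.** - **No success rule is stated.** Section 10.0 never says that a significant ANOVA proves the combination better. If VD works, that ANOVA correctly rejects equality of the four arms, so the percentages above are power for a real VD effect. This stands. They become error rates only if the result is read as evidence for L-cysteine; but the protocol offers no other test of its hypothesis.
- **The hypothesis is joint.** It also requires TNF-α and IR to fall, so a VD-driven signal on 25(OH)VD alone would not establish it. This is true and limits the misleading result to one of three primary endpoints. It does not supply the missing comparison.
- **The SAP may name the contrast.** It could be drawn from the ANOVA or the repeated measures model, and the SAP is not at hand. That would cure the analysis half. It would not make a paired-t sample size apply to a between-arm comparison.
- **The numbers rest on assumptions.** The SD and VD effect are not in the protocol, and sidedness is not stated. One-sided, n=27 implies 0.49 SD and hence a larger SD of about 71 points, under which a two-sided between-arm test would have less power, not more. The rates are illustrations; the logical gap needs none of them.
- **More than 30 may complete.** 160 × 0.84/4 = 33.6 per arm. At 33 per arm, power for 0.56 SD is 61% rather than 57%. Baseline adjustment would add something further. The shortfall shrinks but remains.

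**Conclusion.** The concern holds. The protocol states its hypothesis as VD+LC against VD, then specifies its tests and its 80% power for other questions. That follows from the text and needs no assumed figure.

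The size does depend on assumptions. With SDs back-solved from the protocol's own n, and VD raising 25(OH)VD by 5 to 20 ng/mL, the four-group ANOVA would be significant in 11% to 99.5% of trials in which L-cysteine does nothing. For the comparison of interest, the stated 80% becomes about 57% at the standardised effect implied by n=27, before any gain from baseline adjustment.

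**What to change.** In section 10.0:

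1. Name as the primary test, for the primary endpoints in section 7.0, the between-arm contrast VD+LC minus VD on change from baseline to the end of the 6-month supplementation. Adjust it for the baseline value and report it with a 95% confidence interval.
2. Describe the four-group ANOVA, the within-arm tests and the time-point comparisons as supportive.
3. Say that 7 and 27 refer to change within an arm. State what 30 per arm gives for the contrast: 80% power for about 0.74 SD and about 57% for 0.56 SD, unadjusted.

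The measurement scale and exact model terms can be left to the SAP. So can how the three primary endpoints combine, provided it is settled before unblinding.

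Naming the contrast needs no new data or participants, since baseline values are already collected. The cost is a less favourable power statement: 80% at 0.56 SD would take about 52 per arm. The sponsor would have to accept the lower power openly or address it.

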5.0 Multi-Site Research* N/A (This is only site)

6.0 Study Timelines*

Potential subjects will be contacted over phone or potential subjects may call in response to advertisement and agrees to participate in this study will be asked to come to the clinic after fasting overnight. Fasting blood will be collected after written informed consent. Blood collected at V₋₁ will serve as the sample for the screening visit for the clinical trial. Subjects meeting the inclusion/ exclusion criteria will continue in the clinical trial. All subjects will fill out the complete standard health history before the study and at each visit during the study. This clinical trial will be registered at the ClinTrial.gov site.

Initially, all of the study subjects will be provided placebo supplementation as a placebo run-in period for one month before randomization. Visit 2 (V₀) is for obtaining baseline levels after the run-in period. AA-subjects will be block randomized into four groups. Members of the groups will ingest capsules containing placebo and supplements, orally, daily: (I) placebo (P); (II) LC (1000 mg); (III) VD (2000 IU); (IV) VD and LC. Each capsule will contain a placebo or cholecalciferol (2000 IU) or LC (1000 mg). Placebo group will take two placebo capsules a day in the morning; II LC group will receive two capsules of LC daily; (III) VD group will take two capsules and each capsule will contain 1000 IU VD daily; (IV) VD+LC group will take daily two capsule containing 1000 IU+500 mg LC. Supplements will be taken daily with food at breakfast for 6 months, while participants continue to carry on a normal lifestyle. During the placebo run-in period, all subjects will also take two placebo capsules daily. Based on previous experience, we expect a dropout rate of about 16% as a result of non-compliance, lost contact, taking another medicine, or a subject found to have another disorder. We expect that at least 30 subjects in each group will complete the study. Overnight fasting blood will be collected at each visit. Also, anthropomorphic data, body weight, and height (BMI), the record of any drug use, any adverse effects/complaints (related or unrelated), and Questionnaire will be collected at each visit by the nurse. It is likely to require ~90 minutes to collect the subject's history and other data in interviews with the nurse/dietician and investigators.

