7.0 Study Endpoints*

PROTOCOL TITLE: Optimization of 25(OH) vitamin D levels in African Americans

Primary Endpoints: Blood levels of 25(OH)VD, TNF- α , and HOMA-IR.

Safety Endpoints: Serum calcium (Ca²⁺), PTH, liver, and kidney function tests will be carried out at visits 0, 2, 4, and 6. Whole blood CBC and pregnancy tests will be done at all visits.

Secondary Endpoints: Blood levels of 1,25(OH)₂VD, HbA_{1c}, and pro-inflammatory and anti-inflammatory cytokines (such as IL-2, IL-6, and IL-10).

We will also perform tests to monitor liver and kidney function tests at each visit and complete blood count analyses for any sign of any anemia or unexpected changes in white or red blood cell profiles.

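### If 25(OH)VD change varies more in the vitamin D arms, the four-group ANOVA's pooled error makes the VD+LC versus VD standard error too small

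*Protocol*

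**What the plan says.** Protocol 10.0 gives the between-group analysis in two places: "Data will be analyzed statistically to compare the 4 groups at baseline and various visits using ANOVA", and "the ANOVA test to compare the 4 treatment groups on changes". Covariates, including initial levels, enter a repeated measures model whose residual structure is not described. A p-value "of less than 0.05 for a statistical test will be considered significant".

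Section 6.0 lists the arms as "I) placebo (P); (II) LC (1000 mg); (III) VD (2000 IU); (IV) VD and LC", so two arms receive vitamin D and two do not. Section 1.0 states the hypothesis as a gain of the combination over vitamin D, "suggesting a better therapeutic approach compared with supplementation with VD alone in AA subjects". Section 7.0 lists the primary endpoints as "Blood levels of 25(OH)VD, TNF- α , and HOMA-IR".

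Section 10.0 sizes the trial on a within-group paired t-test (5% level, 80% power) in the VD+LC arm: "a sample size of 7 for 25(OH)VD, and 27 for IR were considered adequate", where the 25(OH)VD target is a mean rise of 30 ng/mL. It aims for 30 completers per arm. No SD of change is given for any arm, and the only pairwise comparisons named are those among time points.

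**The concern.** Ordinary ANOVA assumes the same variance of change in every arm. For 25(OH)VD the design gives reason to doubt this. In the placebo and LC arms, change should be mainly background variation, because supplement users are not enrolled (3.0) and subjects found taking over-the-counter supplements are withdrawn (12.0). In the VD and VD+LC arms, each subject's response to vitamin D is added to that background. Section 1.0 says of high doses in earlier trials that "not all subjects respond to them". Uneven response widens the spread unless it is offset by a negative correlation with background change.

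If the spread does differ, the pooled error averages two large variances and two small ones. A contrast between the two vitamin D arms then gets too small a standard error, too narrow a confidence interval and a false positive rate above 5%. Equal arm sizes do not protect a pairwise contrast. What is at stake is a false claim that adding LC improves 25(OH)VD, one of the primary endpoints.

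**Working it through.** **1. The protocol's n = 7.** It cannot be reproduced forwards because no SD is stated, so I solved backwards. A two-sided paired t-test at 5% with 80% power (noncentral t) needs a standardised change d of 1.273 at n = 7 and 1.435 at n = 6. With a mean rise of 30 ng/mL, the SDs of change that lead to n = 7 run from 30/1.435 = 20.9 to 30/1.273 = 23.6 ng/mL. Sidedness is not stated. At n = 7 a one-sided t-test gives 28.1, and the normal approximation gives 28.3 (two-sided) or 31.9 (one-sided).

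**2. Inputs for the check.**
- Completers per arm: 30 (10.0).
- SD of change with vitamin D: 20.9 to 23.6 ng/mL. This is implied for VD+LC and *assumed* equal in the VD arm.
- SD of change without vitamin D: not given, so *assumed* from 5 ng/mL up to equality.
- No true LC effect.

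**3. Formula.** Let r = SD without vitamin D / SD with vitamin D. With equal arms,

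pooled SE / true SE of VD+LC minus VD = sqrt((1 + r²)/2).

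The approximate two-sided error rate is 2[1 − Φ(1.96 × ratio)].

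**4. One case in full** (SD 23.6 with vitamin D, 10 without):
- True SE = 23.6 × sqrt(2/30) = 6.09.
- Pooled variance = (23.6² + 10²)/2 = 328.5, so pooled SD = 18.1 and pooled SE = 18.1 × sqrt(2/30) = 4.68.
- Ratio = 4.68/6.09 = 0.77.
- Error rate ≈ 2[1 − Φ(1.505)] = 13.2%. Simulation gives 13.3%.

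**5. Range.** Simulated rejection rates, 100,000 null trials per setting, pooled error on 116 df. Each range spans SD 20.9 to 23.6 with vitamin D.

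| SD without vitamin D | r | Pooled SE / true SE | Rejection rate, nominal 5% |
|---|---|---|---|
| 5 | 0.21-0.24 | 0.72-0.73 | 15.5-15.7% |
| 8 | 0.34-0.38 | 0.75-0.76 | 13.6-14.5% |
| 10 | 0.42-0.48 | 0.77-0.78 | 12.5-13.3% |
| 15 | 0.64-0.72 | 0.84-0.87 | 8.9-10.1% |
| 18 | 0.76-0.86 | 0.89-0.93 | 6.7-8.2% |
| equal | 1 | 1.00 | 5.0% |

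Taking the error from the two vitamin D arms alone (58 df) gives 4.8-5.1% throughout. If r exceeded 1 the bias would reverse: at r = 1.25 the pooled SE is 1.13 times too large and the test rejects in 2.7%.

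**6. The test the protocol does state.** The overall F test is much less sensitive. With SDs 8, 8, 22, 22 and equal means it rejects in 6.8%, and about 5-8% over the range considered.

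**The case against.** The strongest reply is that the protocol does not state the test criticised here. It gives an overall four-group comparison, does not name VD+LC versus VD or its error term, and leaves the residual structure of the repeated measures model open. A statistical analysis plan that is not shown could set a Welch contrast. A reader might infer from 10.0 that the key contrast is already committed to the pooled error, or that the trial's false positive rate is known to exceed 5%. The text supports neither. It does support the narrower statement that the method named carries a common-variance assumption which the design makes doubtful, and that the comparison the hypothesis needs is not protected from it.

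The second reply is that unequal spread is assumed. That stands: the SD without vitamin D has no source, and the value implied for VD+LC is carried over to VD alone. The remark on non-response concerns high doses in earlier trials, while 11.0 describes this trial's dose as within a normal range, so it is weak evidence. But for the variances to be equal, subjects taking no vitamin D would need a change SD of about 21 to 24 ng/mL, presumably around a mean near zero, which is hard to credit. The other sizing formulas give larger SDs under vitamin D, which lowers r at any given SD without it.

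Third, the check uses raw change, and adjustment for initial level and BMI may alter the residual SDs. This also stands. What matters then is the ratio of the adjusted SDs, which is unknown.

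Two wider readings should not be drawn:
- *LC versus placebo loses nearly all its power on 25(OH)VD.* The pooled error is too large for that contrast, but the loss depends on the assumed SD. With SD 22 under vitamin D, a contrast with 80% power on its own two-arm error keeps about 0.1%, 12%, 31% or 64% at SD 5, 8, 10 or 15. It is also not the stated hypothesis.
- *The same holds for 1,25(OH)₂VD.* Nothing in the protocol supports a variance argument for it.

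**Conclusion.** The point holds conditionally. If change in 25(OH)VD varies more in the two vitamin D arms, as the design suggests but no stated SD shows, a VD+LC versus VD comparison using the pooled ANOVA error is anti-conservative. The false positive rate is roughly two to three times nominal for SDs of 5 to 15 ng/mL without vitamin D, falls to 7-8% at 18, and is correct at equality. These figures rest on 30 completers per arm, a two-sided reading of n = 7, the same SD in both vitamin D arms, and unadjusted change. A reader might conclude that the four-group ANOVA itself is invalid, but the overall F test is only mildly disturbed. This is an inexpensive improvement to the trial's main comparison and should be made; it is not a demonstrated error in a stated result.

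**What to change.** In 10.0, for 25(OH)VD, name the VD+LC versus VD contrast on change and state that it will be estimated with unequal variances allowed. This can be a Welch contrast, or a residual variance specific to each arm in the repeated measures model, so that the error of the contrast comes from those two arms.

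This takes one sentence and one model option. If the variances turn out equal, the loss is about 58 instead of 116 degrees of freedom, a critical value of 2.00 instead of 1.98. No change to the sample size or the data collected is needed for this.

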3.0 Inclusion and Exclusion Criteria*

Informed written consent will be obtained from all subjects according to the IRB approved protocol. All subjects in this study will be adult AA volunteers and will meet the inclusion/exclusion criteria given below.

INCLUSION CRITERIA: (1) African-American adults aged 18-65 years willing to participate in 5 clinic visits where blood will be drawn; (2) participants who demonstrate an understanding of the risks and benefits of the protocol and sign the informed consent form; (3) participants willing to complete standard health history questionnaire before and during the study (**Copy enclosed**); (4) women with negative pregnancy tests (pregnancy test will be performed on all women participants)

EXCLUSION CRITERIA: (1) History of cardiovascular disease, sickle cell disease, or metabolic disorders including: diabetes, uncontrolled hypertension, hypothyroid, or hyperthyroid; (2) any sign of hepatic dysfunction or renal dysfunction, hypercalcemia, or nephrolithiasis; (3) those taking antiepileptic medications, glucocorticoids, or weight loss or other dietary supplements within the two months previous to enrollment or during the study; (4) those who visit tanning booths; (5) any subject who develops an infection and has to take antibiotics; and (6) women with positive pregnancy tests or those who are nursing. (7) adults unable to consent or prisoners. Any subject taking vitamin D or any other vitamin

PROTOCOL TITLE: Optimization of 25(OH) vitamin D levels in African Americans

or herbal supplement even advised by a doctor or over-the-counter will not be enrolled in the study.

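### On its natural reading, the repeated measures model uses the V0 value both as a response and as a plain covariate, so the promised baseline adjustment adds no precision to the between-arm comparison of change

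*Protocol*

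**What the plan says.** Section 10.0 describes a repeated measures analysis in two adjacent sentences. On change over time: "The results for the pairwise comparisons among the 4 time points will determine whether there is a significant change" in the outcomes. On adjustment, it says that "covariates or possible confounders (age, sex, BMI, initial levels of outcomes, etc.) will be controlled for" and that this is done "by including them in the repeated measures model used". It names no covariate-by-time term, does not list the four time points, and does not say which contrast between arms will be read from the model.

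The same section gives a separate between-arm test, an analysis of variance of the changes across the four arms. It attaches no covariates to that test.

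The visit structure comes from three other places:
- Section 3.0 asks for people "willing to participate in 5 clinic visits where blood will be drawn".
- Section 6.0 makes V-1 the screening sample and says that V0 "is for obtaining baseline levels after the run-in period".
- Section 7.0 says that the safety blood tests "will be carried out at visits 0, 2, 4, and 6".

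**The concern.** The objective in section 1.0 is a comparison of arms: VD+LC against VD alone. The repeated measures model is the only analysis in section 10.0 that promises adjustment for the starting level, and such adjustment normally makes this comparison more precise.

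If V0 is one of the responses and the V0 value is also a covariate with a single slope, the adjustment drops out of the contrast that measures change from V0. The plan would then say that baseline is controlled for, while the between-arm comparison of change keeps the precision of an unadjusted change score. With a goal of 30 completers per arm, that loss is worth avoiding.

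A second question is what happens if the arm effect averaged over all visits is reported, since one of the four averaged points precedes any supplement.

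**Working it through.** **Which four time points.** Five blood-draw visits (3.0) less screening V-1 (6.0) leaves four: V0 and three later ones. Section 7.0 labels them 0, 2, 4 and 6, although only for the safety tests. I take these labels as months, since section 6.0 numbers the V0 visit differently, as Visit 2. Without V0 only three points remain, so four points used to judge change must include V0 or, less plausibly, V-1.

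**The plan's own figures.** The protocol gives none for this model. Its sample sizes (7 for 25(OH)VD, 27 for IR) are for a paired t-test within one arm. They cannot be reproduced because no SD is stated, and nothing below uses them.

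**The covariate and the change contrast.** For subject i in arm a at visit t, write the mean as μ_t + α_a + γ_at + β·b_i, where b_i is the initial level. The V6 mean minus the V0 mean is (μ_6 − μ_0) + (γ_a6 − γ_a0). The term β·b_i has gone, because it is the same at every visit. With complete data the cancellation is exact.

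A numerical check used one simulated trial: four arms of 30, SD 1, equal correlation 0.6 between visits, and a random-intercept model.
- No covariate: contrast 0.85047, SE 0.2099.
- V0 as a main effect: contrast 0.85047, SE 0.2099.
- V0 and V0-by-time: contrast 0.85477, SE 0.1991. The estimate equals that from analysis of covariance at V6 (0.85477).

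**Size of the lost precision.** Assume equal variance σ² at V0 and V6, and correlation r. A change score has residual variance 2(1−r)σ². Analysis of V6 with V0 as covariate has (1−r²)σ². The ratio is 2(1−r)/(1−r²) = 2/(1+r). The protocol gives no r, so a range is shown.

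| Assumed r | 2(1−r) | 1−r² | Ratio | 30 per arm do the work of 30(1+r)/2 |
|---|---|---|---|---|
| 0.3 | 1.40 | 0.91 | 1.54 | 19.5 |
| 0.5 | 1.00 | 0.75 | 1.33 | 22.5 |
| 0.7 | 0.60 | 0.51 | 1.18 | 25.5 |

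In 2000 simulated comparisons of 30 with 30 at each r, the mean SEs for change score and covariance analysis were 0.3037 and 0.2470, 0.2566 and 0.2240, and 0.1996 and 0.1856. The squared ratios are 1.51, 1.31 and 1.16, slightly below the formula because the slope has to be estimated.

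**The four-visit average.** The mean of four visits is (V0 + 3 × post-baseline mean)/4. Once V0 is in the model as covariate, the V0 part carries no arm effect and no residual. Both the estimate and its SE are therefore multiplied by 3/4. In the simulated trial:
- Responses V2, V4 and V6: estimate 0.796, SE 0.1367, t = 5.83.
- Responses V0, V2, V4 and V6: estimate 0.597, SE 0.1025, t = 5.83.

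Across 2000 replicates at r = 0.5 and a true effect of 0.5 SD, power was 0.8425 both ways.

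**The case against.** The strongest reply is that the double role is inferred. Section 10.0 does not list the four time points or say that V0 is a response in this model. The visit labels in section 7.0 belong to the safety tests, and the initial level could mean the V-1 sample. Model details of this kind are often settled in a statistical analysis plan, which is not at hand. This stands as a limit on certainty, but two things weaken it. Section 6.0 assigns baseline to V0. And if V-1 were meant, the covariate would still be constant within a subject and would still cancel from V6 minus V0; only the exact equal scaling of the four-visit average would go.

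Several stronger readings are tempting and should not be drawn:
- **That adjustment can have no effect in any form of the model.** With a V0-by-time term the contrast equals the covariance-analysis estimate. Section 10.0 names no such term but does not exclude one. With V0 still a response, though, that form fits V0 exactly, so the model's single residual variance is wrong and its SE is not a sound guide.
- **That including V0 in the average weakens the test.** Estimate and SE shrink together, so t, p and power are unchanged. The protocol also does not say that this average will be reported.
- **That the analysis is biased or its error rate wrong.** With randomised arms, an unadjusted change-score contrast is valid.
- **That a power can be put on the VD+LC versus VD comparison.** The only effect size that can be back-solved is about 0.56 SD of change, from n = 27 (two-sided). It concerns change within one arm. The protocol states no between-arm effect or SD, so no absolute power is supportable.

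It may also be said that the named between-arm test of change is the separate analysis of variance. That is correct, but it is unadjusted as described, so it does not supply the missing precision. The repair must cover it too.

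**Conclusion.** The point holds as one of efficiency, not validity. As section 10.0 is most naturally read, neither between-arm analysis of change gains from the baseline value: in the repeated measures model the covariate cancels, and in the analysis of variance of changes it is absent. The variance is 1.54, 1.33 or 1.18 times what baseline adjustment would give at r = 0.3, 0.5 or 0.7.

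This rests on four assumptions: V0 is among the four responses, the covariate enters as a main effect only, variances at V0 and V6 are equal, and r lies in the range shown. The 0.75 factor concerns only the size of a reported four-visit average. The matter is moderate to minor in weight, but the gain is free because V0 is already collected.

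**What to change.** Rewrite the repeated measures sentences in section 10.0 so that V0 has one role only. Either form will do:
- Use visits 2, 4 and 6 as responses. Fit arm, visit and arm-by-visit, with the V0 value and V0-by-visit as covariates.
- Keep V0 with visits 2, 4 and 6 as responses, constrain the arms to a common mean at V0, use an unstructured within-subject covariance, and enter no V0 covariate.

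State that VD+LC versus VD at visit 6 (month 6) is read from this model, and that it replaces the unadjusted analysis of variance of changes for the between-arm comparison. If a statistical analysis plan exists, give the same model there.

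The cost is a few sentences of analysis wording, with no extra subjects, visits, blood or assays.
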